Secondary Endpoints	 Incidence of confirmed SARS-CoV-2 detection Incidence of possible COVID19 symptoms Incidence of all-cause study medicine discontinuation Ordinal Scale of COVID-19 Disease maximum severity if COVID-19 diagnosed Incidence of Hospitalization for COVID-19 or death Incidence of study medication-related side effects 	
Duration of Participation	• Recruitment and follow up will be internet-based. All patients will be followed for at least 4 weeks. Recruitment is expected to take 4 weeks, for a total study duration of 8 weeks. But the total study duration will depend on the actual rate of enrollment. Study drug will be given for a maximum of 12 weeks.	
Inclusion Criteria	 Healthcare worker, at high risk of COVID-19 exposure: Persons primarily working in emergency departments (physicians, nurses, ancillary staff, triage personnel) Persons primarily working in intensive care units (physicians, nurses, ancillary staff, respiratory therapists) Persons performing aerosol generating procedures: ex. Anesthesiologists, nurse anesthetists (CRNAs) First responders: ex. EMTs, paramedics 	
	 Age >=18 years of age Provision of Informed Consent 	
Exclusion Criteria	 Active COVID-19 disease Confirmed prior COVID-19 disease Current fever, cough, shortness of breath Contraindication or allergy to chloroquine or hydroxychloroquine Prior retinal eye disease Known Chronic Kidney disease, Stage 4 or 5 or dialysis. Known glucose-6 phosphate dehydrogenase (G-6-PD) deficiency. Weight <40 kg Current use of hydroxychloroquine or cardiac medicines of flecainide, amiodarone, digoxin, procainamide, or propafenone Current use of medications with known significant drug-drug interactions: artemether, lumefantrine, mefloquine, tamoxifen, or methotrexate. 	

Statistical	 10% transmission rate for high-risk healthcare workers with		
Assumptions	no treatment		
	 Alpha = 0.025 (to account for two treatment groups vs. placebo comparisons) Assuming 15% lost to follow up in the placebo group and 5% lost to follow up in each treatment group N=3500 has 80% power to detect a hazard ratio of 0.65, using a two-sided log-rank test 		

Schematic of Study Design:

At the close of the study, any participant with ongoing illness will continue to be assessed for up to a total of 90 days after the common closing date.

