2 BACKGROUND INFORMATION AND SCIENTIFIC RATIONALE

2.1 Background Information

Significance of Research Question/Purpose:

Severe acute respiratory syndrome coronavirus 2 (SARS-CoV-2) is a rapidly emerging viral infection causing COVID-19. The current strategy uses a public health model of identifying infected cases, isolation, and quarantine to stop transmission. Once exposed, observation is standard-of-care.

No effective therapy currently exists for treatment. The lack of effective therapy diminishes persons presenting for self-quarantine. Having an effective pre-exposure prophylaxis for healthcare workers at high risk of contracting COVID-19, even if only partially effective, may additionally create synergy for the public health strategy of case identification and isolation – if a safe prophylaxis is available.

People who develop COVID-19 disease generally develop signs and symptoms, including mild respiratory symptoms and fever, after an average of 5-6 days after exposure (i.e. mean incubation period). The range of the incubation period is between 1 to 14 days.¹

Most people infected with the COVID-19 virus have mild disease and recover. Approximately 80% of laboratory-confirmed patients have had mild to moderate disease, which includes non-pneumonia and pneumonia cases, 14% have severe disease, and 6% are critically ill with respiratory failure, shock, and/or multiple organ dysfunction.²

Preliminary Data:

Chloroquine has *in vitro* activity in cell lines against SARS-CoV and SARS-CoV2. In a Vero E6 cell line, the half-maximal effective concentration (EC50) activity of chloroquine was 1.13 µM against SARS-CoV2.³ Hydroxychloroquine is functionally equivalent as chloroquine.

Another compound under treatment trials, remdesivir (Gilead) had an EC50 of 0.77 µM.³ Remdesivir (Gilead) is not FDA-approved and in limited quantities. Hydroxychloroquine is FDA-approved and globally is inexpensive. Chloroquine is no longer broadly available in the USA.

Existing Literature:

Several drugs, such as ribavirin, interferon, lopinavir-ritonavir, corticosteroids, have been used in patients with SARS or MERS, although the efficacy is poorly understood as a gold standard randomized clinical trial has not been conducted.

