3.2.2 Secondary Outcome Measures

- Incidence of confirmed SARS-CoV-2 detection
- Incidence of symptoms compatible with COVID19 (possible disease)
- Incidence of all-cause study medicine discontinuation or withdrawal
- Ordinal Scale of COVID-19 Disease Severity (for those who develop COVID-19)
 - No illness
 - Illness with outpatient observation
 - Hospitalization (or post-hospital discharge)
 - Hospitalization with ICU stay or death
- Incidence of hospitalization or death
- Self-reported adherence
- Self-reported study medication side effects

Primary outcome of COVID-19-free survival will be confirmed by positive test. Assessment of other outcome measures will be primarily by self-report. As necessary, COVID-19 disease will be verified from public health records, medical records, or death certificates.

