8.2 Methods and Timing for Assessing, Recording, and Analyzing Safety Parameters

8.2.1 Adverse Events

Hydroxychloroquine has an excellent safety track record, being first FDA-approved in 1955. Adverse events will not be captured unless they result in hospitalization. See Serious Adverse Events below.

Expected adverse events would include normal events within the general population as well as COVID19-related disease events which may include the need for hospitalization, pneumonia, respiratory failure, sepsis, and death.

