8.3.1 Serious Adverse Events

An AE or suspected adverse reaction is considered a serious adverse event (SAE) if it results in any of the following outcomes:

PREP COVID-19

- Death,
- a life-threatening adverse event (as below),
- hospitalization,
- a persistent or significant incapacity or substantial disruption of the ability to conduct normal life functions, or
- congenital anomaly/birth defect.
- Important medical events that may not result in death, be life-threatening or require hospitalizations may be considered serious when based upon appropriate medical judgment they may jeopardize the participant or subject and may require medical or surgical intervention to prevent one of the outcomes listed in this definition.
- Examples of such medical events include allergic bronchospasm requiring intensive treatment in an emergency room or at home, blood dyscrasias or convulsions that do not result in inpatient hospitalization, or the development of drug dependency or drug abuse.
- Life-threatening adverse event. An AE is considered "life-threatening" if, in the view of either the site principal investigator or sponsor, its occurrence places the subject at immediate risk of death. It does not include an AE that, had it occurred in a more severe form, might have caused death. For life-threatening AEs, subjects would be recommended /expected to be hospitalized.

Based on the known safety track record of hydroxychloroquine, this pragmatic protocol will focus on death, life-threatening AEs, and hospitalizations. Incapacity / permanent disability is a possibility with COVID19, but this is not associated with hydroxychloroquine. In the event of incapacity, the subject would be expected to be hospitalized.

Hydroxychloroquine and chloroquine are not known to cause teratogenic events and are viewed as safe in pregnancy, especially with short term use. With this trial's sample size, this will not further delineate this risk. COVID-19 disease may indeed be teratogenic. For women who are pregnant, we will ask to follow them through the end of their pregnancy.

Thus the hospitalization or death secondary endpoint will capture relevant SAEs.

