10.2 Sample Size Considerations

The planned sample size is up to 3500 participants. There will be two comparisons: treatment once weekly compared to placebo, and treatment twice weekly compared to placebo. With 1165 participants in each of the two treatment groups and in one placebo group, a two-sided log-rank test achieves 80% power at alpha = 0.025 significance level to detect a hazard ratio of 0.65 when COVID-19 free survival is 90% in the placebo group.

The study is powered at alpha = 0.025 to account for the two treatment versus placebo comparisons. The two treatment groups will be compared to the same placebo group. Assumed loss to follow-up is 5% in the treatment groups and 15% in the placebo group. With 3500 participants approximately 310 COVID-19 or death events are anticipated.

Sample Size Re-estimation:

At the time of the second DSMB review, a sample size re-estimation will occur based on the disease transmission rate in the control group. The conservative *a priori* assumption (based on limited data) is 10% transmission risk. The table below shows that if the transmission rate is 8% (lower than assumed) then the sample size would need to be increased to a total of 4353 participants. On the other hand, if the transmission rate is greater than the assumed 10% then the sample size can be decreased.

Sample size requirements to detect a hazard ratio of 0.65 based on COVID19 transmission rates without treatment (assuming 80% power, alpha = 0.025, 15% loss to follow-up in the placebo group and 5% loss to follow-up in the treatment groups)

COVID 19 Transmission Rate Without Treatment	Number Per Group	Total Sample Size (3 Groups)
8%	1451	4353
10%	1163	3489
12%	971	2913
15%	778	2334
18%	650	1950
20%	580	1740

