10.4 Final Analysis Plan

We will assessCOVID-19-free survival in high-risk healthcare workers who receive hydroxychloroquine compared to those who receive placebo.

We will compare survival in a time-to-event analysis for COVID-19-free survival using Log-rank test with survival displayed as a Kaplan-Meier curve. Analysis will be intention-to-treat. Persons who develop confirmed COVID-19 or die will be considered failures. Persons lost to follow up will be censored.

Secondary endpoints for incidence will be assessed via Fisher's Exact test for the proportions by study arm. The secondary endpoint on the ordinal scale will be assessed with a proportional odds model.

PREP COVID-19

Version 1.0 27 March 2020

Among those with symptoms, severity of symptoms (recorded on a 0-10 visual analog scale) will be compared via Mann-Whitney U by study arm.

A priori subgroup analyses will include assessment by:

- Days from Exposure
- Decile of age
- Sex as a biological variable
- Censored subjects, who became symptomatic before receipt of the first dose of study medicine, will be separately analyzed and reported.

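### Serious harm is captured only inside an any-cause hospitalisation-or-death endpoint, so COVID-19 admissions dilute, and may offset, a drug-caused excess; no by-arm comparison of non-COVID events is planned

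*Combined protocol and SAP*

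**What the plan says.** Section 8.2.1 sets the capture rule: "Adverse events will not be captured unless they result in hospitalization". It counts among the expected adverse events "COVID19-related disease events which may include the need for hospitalization, pneumonia, respiratory failure, sepsis, and death". Section 8.3.1 defines serious adverse events, narrows the focus to deaths, life-threatening events and hospitalisations, and ends: "Thus the hospitalization or death secondary endpoint will capture relevant SAEs".

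The endpoint it refers to is listed in Section 3.2.2 as "Incidence of hospitalization or death", with no cause attached. The Summary table has a different endpoint, "Incidence of Hospitalization for COVID-19 or death".

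For the analysis, Section 10.4 states: "Secondary endpoints for incidence will be assessed via Fisher's Exact test for the proportions by study arm". Section 10.3 has secondary endpoints reported descriptively at interim looks and does not mention cause.

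**The concern.** The endpoint carries two opposite signals. Under the hypothesis in Section 10.1, the drug prevents COVID-19 and makes it milder, so COVID-19 admissions fall on drug. Any admissions that the drug causes push the same total up. The null hypothesis of the Fisher test is equal totals, and that can be true while the drug is putting people in hospital.

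Even without benefit, COVID-19 admissions add events unrelated to drug toxicity and bury a small excess in noise.

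This matters because participants are well at entry and, on the plan's own assumption, 90% of the placebo group stay free of COVID-19. Whether the drug causes serious events in such people is a separate question from its net effect on admissions. Recording a serious event inside a composite does not ensure that an excess can be seen.

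**Working it through.** **The plan's own figure.** The documents give no event count or power for hospitalisation or death, so there is nothing to reproduce for this endpoint. I take the arm size from Section 10.2 as planned: "With 1165 participants in each of the two treatment groups and in one placebo group". (The 1163 in the Section 10.2 table is not reproduced at the stated two-sided 0.025. Schoenfeld's formula needs 205 events per comparison, or 1234 per arm before any loss. That is a separate matter and does not affect this point.)

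**Inputs from the documents.**
- Placebo COVID-19 risk is 10% and the hazard ratio is 0.65 (Section 10.2). The active-arm risk is 1 − 0.90^0.65 = 6.62%.
- The severity mix in Section 2.1 is "14% have severe disease, and 6% are critically ill", which sums to 20%.

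**Assumptions, because the documents give no figure.**
- Share of COVID-19 cases admitted, s: 20% (treating severe plus critical as admitted), 10% or 5%, the same in all arms.
- Background non-COVID admissions, b: 0.5% (range 0.25% to 1.0%).
- Drug-caused admissions, d: +0.68, +1.0 or +1.5 points.
- Two-sided 0.05 for the Fisher test, since no level is stated for secondary endpoints.
- No loss to follow-up.

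**Step 1: admissions averted.** With s = 20%, placebo has 1165 × 0.10 × 0.20 = 23.3 COVID-19 admissions and an active arm has 1165 × 0.0662 × 0.20 = 15.4. The difference is 7.9, or 0.68 points. With s = 10% it is 3.9 (0.34 points).

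**Step 2: event probabilities.**
- Mixed endpoint: placebo 0.10s + b; drug 0.0662s + b + d.
- Mixed endpoint, no benefit: placebo 0.10s + b; drug 0.10s + b + d.
- Non-COVID events only: placebo b; drug b + d.

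**Step 3: exact power.** Sum the product of the two binomial probabilities (n = 1165 each) over all pairs of counts where the drug count is higher and Fisher's two-sided p is at most 0.05.

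Results for d = +1.0 point and b = 0.5%:

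| Cases admitted | Expected mixed events, placebo v drug | Power, mixed | Power, mixed, no benefit | Power, non-COVID only (5.8 v 17.5) |
|---|---|---|---|---|
| 20% | 29.1 v 32.9 | 5.5% | 26% | 62% |
| 10% | 17.5 v 25.2 | 18% | 35% | 62% |
| 5% | 11.7 v 21.3 | 33% | 45% | 62% |

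**Step 4: sensitivity.**
- s = 20%, b = 0.5%, d = +0.68: expected totals are 29.1 v 29.2, and power is 2% mixed v 35% non-COVID. With no benefit the mixed figure is 14%.
- s = 20%, b = 0.5%, d = +1.5: 19% v 90%.
- s = 5%, b = 0.5%, d = +0.68: 15% v 35%.
- s = 20%, d = +1.0, b from 0.25% to 1.0%: 5% to 6% mixed v 77% down to 45% non-COVID.
- d = +0.68, b from 0.25% to 1.0%: non-COVID power falls from 49% to 24%.
- s = 20%, b = 0.5%, d = +1.0, at a level of 0.025: 3% v 51%.

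**Step 5: dilution or offset.** For s = 20%, b = 0.5% and d = +1.0, power falls from 62% to 26% through dilution alone (36 points), then to 5.5% when benefit offsets harm (a further 20 or so). Dilution is the larger part.

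**The case against.** The strongest reply is that safety does not rest on this one endpoint. SAEs are queried on Day 1, weekly and at termination (Sections 4.3.3 to 4.3.5). Side effects and discontinuation are separate outcomes. Section 8.3.2 has an independent medical monitor judge relatedness, and a DSMB oversees the trial. The ordinal scale in Section 3.2.2 records hospitalisation among people who develop COVID-19, so non-COVID admissions could be approximated by subtraction.

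All of that stands as data collection. None of it is a planned by-arm comparison of serious events with COVID-19 removed. The route in Section 8.3.2 works case by case and leaves out events expected with COVID-19 or listed in the package insert; Section 2.3.1 lists convulsions and fulminant hepatic failure from that insert.

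A reader might infer two stronger things that the documents do not support.
- *That safety will be judged by a non-significant Fisher test.* Section 8.3.1 speaks of capturing events, and Section 10.4 applies the test to all incidence endpoints alike. Neither states such a rule.
- *That benefit and harm generally cancel, leaving almost no power.* Full cancellation needs harm close to the admissions averted. The 2% figure is the case where harm was set equal to benefit. With 5% of cases admitted, power at +1.0 point is 33%.

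It is also fair that the size of harm is assumed: +0.68 to +1.5 points is 8 to 17 drug-caused admissions per arm, against about 6 in the background. All-cause hospitalisation or death remains a legitimate net measure. Outcomes are mainly self-reported and the tablets are not identical (Section 5.3.2), so a self-reported reason for admission could be influenced by arm.

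**Conclusion.** The point holds as a gap in the analysis plan for serious harm; self-reported side effects are a separate outcome. The only planned by-arm comparison of serious events mixes COVID-19 admissions with all others. That always dilutes a drug-caused excess, and it offsets the excess to the extent that the drug works. The non-COVID comparison had higher power in every scenario tried, but the size of the gap depends on the assumed admission share, background rate and harm.

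Separately, the Summary's wording excludes non-COVID admissions. Under it there is little to dilute or offset, because the endpoint misses those admissions outright. It conflicts with Section 3.2.2 and with the reliance placed on the endpoint in Section 8.3.1, and the three must be reconciled. Choosing the any-cause wording does not remove the dilution.

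Separation is an improvement and not a guarantee: at +0.68 points it gives about 24% to 49% power. That is why an interval is more useful here than another significance test.

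**What to change.** Reconcile the Summary, Section 3.2.2 and Section 8.3.1 on what the endpoint contains. In Sections 8.3.1 and 10.4, state that the reason for each admission or death is recorded and classified blind to arm, using medical records where consent allows (Section 11). For each dose against placebo, report:

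- **Safety comparison:** hospitalisation or death not due to confirmed COVID-19, as a risk difference with 95% confidence interval. Add a sensitivity analysis that also removes suspected COVID-19. Removing suspected cases from the main comparison could discard real drug harm in people with compatible symptoms.
- **Efficacy:** hospitalisation or death due to COVID-19.
- **Net summary:** all-cause hospitalisation or death.

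Use the same split in reports to the DSMB.

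The cost is some wording, one question added to the existing hospitalisation query, blinded classification of a small number of events, and one table. Sample size and treatment are unchanged. The downside is that some admissions will be hard to classify and the self-reported reason may be imperfect; the retained all-cause line covers this.

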8.3.2 Regulatory Reporting

As hydroxychloroquine is an FDA-approved medicine being used at standard dosing for malaria prophylaxis, reporting to regulatory authorities will occur in summary format after each DSMB reports and at a frequency of at least annually.

Serious unexpected suspected adverse reactions (SUSARs) which are not expected with COVID19 nor listed in the FDA package insert will be reported to the IRB.

Those SUSARS which are deemed by an independent medical monitor to be related to the study medication will be reported to the FDA and IRB.

8.3.3 Reporting of Pregnancy

Chloroquine and hydroxychloroquine are not known to be teratogenic. Chloroquine and hydroxychloroquine can accumulate in neonatal eyes. Conversely, the risk of severe COVID-19 infection is unknown, but could represent a heightened risk in pregnant women. The CDC states, "We do not have information on adverse pregnancy outcomes in pregnant women with COVID-19. Pregnancy loss, including miscarriage and stillbirth, has been observed in cases of infection with other related coronaviruses (SARS-CoV and MERS-CoV) during pregnancy. High fevers during the first trimester of pregnancy can increase the risk of certain birth defects."

Thus, the risk/benefit would favor the enrollment of women who may be or are pregnant, so as to not discriminate against pregnant women.

For women who are pregnant, we will ask to have follow through until the end of their pregnancy to assess the outcome of the pregnancy via a brief survey.

8.4 Type and Duration of Follow-up of Subjects after Adverse Events

Participants who are hospitalized for COVID-19 or SAEs will have up to 90 day follow up after the common closing date, to assess their final outcome. Management will be as per the participant's local healthcare provider.

8.5 Safety Oversight (DSMB)

A data and safety monitoring board (DSMB) will oversee the trial. The quorum will include three members and a biostatistician. The PI will be a non-voting observer, providing input as requested.

9 CLINICAL MONITORING

Clinical site monitoring is conducted to ensure that the rights and well-being of trial subjects are protected and that the reported trial data are accurate, complete, and verifiable. Clinical monitoring also ensures that the conduct of the trial is in compliance with the currently approved protocol/ amendment(s), ICH, GCP, and with applicable regulatory requirement(s) and Sponsor requirements. Clinical monitoring will also verify

that any critical study procedures are completed following specific instructions. Monitoring will be the responsibility of the University of Minnesota.

10 STATISTICAL CONSIDERATIONS

10.1 Study Hypotheses

We hypothesize that Hydroxychloroquine is superior to placebo for preventing COVID-19 disease. We hypothesize, that if COVID-19 develops while a person is taking hydroxychloroquine prophylaxis, then the COVID-19 disease would be less severe.

10.2 Sample Size Considerations

The planned sample size is up to 3500 participants. There will be two comparisons: treatment once weekly compared to placebo, and treatment twice weekly compared to placebo. With 1165 participants in each of the two treatment groups and in one placebo group, a two-sided log-rank test achieves 80% power at alpha = 0.025 significance level to detect a hazard ratio of 0.65 when COVID-19 free survival is 90% in the placebo group.

The study is powered at alpha = 0.025 to account for the two treatment versus placebo comparisons. The two treatment groups will be compared to the same placebo group. Assumed loss to follow-up is 5% in the treatment groups and 15% in the placebo group. With 3500 participants approximately 310 COVID-19 or death events are anticipated.

Sample Size Re-estimation:

At the time of the second DSMB review, a sample size re-estimation will occur based on the disease transmission rate in the control group. The conservative *a priori* assumption (based on limited data) is 10% transmission risk. The table below shows that if the transmission rate is 8% (lower than assumed) then the sample size would need to be increased to a total of 4353 participants. On the other hand, if the transmission rate is greater than the assumed 10% then the sample size can be decreased.

Sample size requirements to detect a hazard ratio of 0.65 based on COVID19 transmission rates without treatment (assuming 80% power, alpha = 0.025, 15% loss to follow-up in the placebo group and 5% loss to follow-up in the treatment groups)

COVID 19 Transmission Rate Without Treatment	Number Per Group	Total Sample Size (3 Groups)
8%	1451	4353
10%	1163	3489
12%	971	2913
15%	778	2334
18%	650	1950
20%	580	1740

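### Holm over the two dose comparisons keeps familywise error at 0.05 and, if both doses work, adds about 5 points of power per dose over the fixed 0.025 split; 10.4 should name the two comparisons

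*Combined protocol and SAP*

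**What the plan says.** Section 10.2 defines the family of tests: "There will be two comparisons: treatment once weekly compared to placebo, and treatment twice weekly compared to placebo". One control group serves both: "The two treatment groups will be compared to the same placebo group". The alpha is divided in advance: "The study is powered at alpha = 0.025 to account for the two treatment versus placebo comparisons". The Statistical Assumptions row of the Summary gives the same reason for 0.025. The sizing claim is that "a two-sided log-rank test achieves 80% power at alpha = 0.025 significance level to detect a hazard ratio of 0.65". That claim takes the placebo event risk to be 10%.

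Section 10.3 builds one table of O'Brien-Fleming-type boundaries at an overall alpha of 0.025, with a final critical value of 2.30. It does not say which comparison the table applies to.

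Section 10.4, which governs the final test, describes a single contrast: "high-risk healthcare workers who receive hydroxychloroquine compared to those who receive placebo". It specifies a log-rank test and intention-to-treat analysis. It does not separate the doses, give an alpha or state a multiplicity rule.

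Sections 5.3.5 and 10.3 convert the trial to an open-label cohort if it is halted for efficacy.

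**The concern.** Under a fixed split, once one dose is significant the other must still clear 0.025, although its null hypothesis is then the only one left to protect. Holm would test it at 0.05 with the same strong control of familywise error. The trial carries two regimens because, as section 2.2 says, the effective dosing is unknown, so the chance of reaching a conclusion on each dose matters.

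Section 10.4 also leaves the choice of test less tightly bound than it should be before unblinding. Read alone, it fits two pairwise tests, a three-group log-rank test or one pooled active-versus-placebo test. These answer different questions, and only the first was sized.

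**Working it through.** **Inputs (10.2).** Two-sided alpha 0.025 per comparison; hazard ratio 0.65, ln = −0.4308; 1165 per group; loss 15% placebo and 5% per treatment group. Placebo event risk is 10%, so treated risk is 1 − 0.9^0.65 = 6.62%. Critical values are 2.2414 (0.025) and 1.9600 (0.05).

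**Step 1. The plan's own figure.** Schoenfeld events for 80% power: 4 × (2.2414 + 0.8416)² / 0.4308² = 204.9, so 205.
- Stated losses: 205 / (0.10 × 0.85 + 0.0662 × 0.95) = 205 / 0.1479 = 1386 per group.
- No loss: 205 / 0.1662 = 1234 per group.

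Neither matches the 1163 in the table or the 1165 in the text. With the stated losses, 1165 per group gives 1165 × 0.1479 = 172 events per comparison and power Φ(√172.3 / 2 × 0.4308 − 2.2414) = Φ(0.586) = 72.1%. Log-rank simulation gives 73.4%. With the stated losses, the table's 10% row is approached using 1.9600 in place of 2.2414: 170 / 0.1479 = 1150. That is a separate issue. Both starting points, the stated 80% and the recomputed value, are carried below.

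**Step 2. Power under each rule, both doses at 0.65, single final look.**
- Fixed split, per dose: P(Z1 > 2.241).
- Holm, per dose: P(Z1 > 2.241) + P(1.960 < Z1 ≤ 2.241 and Z2 > 2.241).
- Sharing the placebo group correlates Z1 and Z2: ρ = (1/d0) / (1/d0 + 1/d1), where d0 and d1 are placebo and treated events. This gives about 0.40 to 0.43; the 80% row uses 0.40 to 0.50.

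The lower three rows use the variance 1/d0 + 1/d1 at 1165 per group.

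| Starting point | Events d0 / d1 | Per dose, split → Holm | Both doses, split → Holm |
|---|---|---|---|
| Stated 80% | – | 80.0% → 84.6–84.8% | 67.6–68.7% → 77.2–77.8% |
| No loss | 116.5 / 77.1 | 75.6% → 80.8% | 61.5% → 71.9% |
| Half the stated loss | 107.8 / 75.2 | 73.4% → 78.7% | 58.8% → 69.4% |
| Full stated loss | 99.0 / 73.3 | 71.0% → 76.4% | 55.9% → 66.7% |

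The gain per dose is 4.6 to 4.8 points from 80% and 5.2 to 5.4 in the lower rows. From the Schoenfeld 72.1%, Holm reaches 77.3–77.4%. The gain for both doses is about 9 points from 80% and 10 to 11 in the lower rows.

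**Step 3. Other truths, starting from 80%.**
- Other dose null: the effective dose stays at about 80%, a gain of 0 to 0.2 points.
- Other dose at 0.80: the 0.65 dose gains 0.8 points, the weaker dose 8.7 (26.0% to 34.7%).
- At least one dose significant: unchanged in every case, because Holm's first step is the 0.025 test itself.

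**Step 4. Error rate.** With both nulls true, the chance of any rejection is 0.047 under both rules (ρ = 0.45). With one dose effective, Holm rejects the null dose 4.3% of the time, against a limit of 5%.

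**Step 5. Four looks.** Carrying Holm through O'Brien-Fleming-type boundaries gives 79.0% → 83.5% per dose, a gain of 4.5 points. A second simulation used the half-loss case and the 10.3 boundaries. It assumed that information tracks enrolment, that one dose crossing halts the trial, and that the other dose is then tested on the data in hand. About 57% of trials halt early, and power for both doses is about 24% (split) against 39% (Holm).

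**The case against.** The strongest reply is that nothing is wrong with the chosen method. A fixed split controls familywise error, and 10.2 states the two comparisons clearly. That stands: this is a point about efficiency.

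The benefit is also conditional, and that stands too. The objective (3.1) and hypothesis (10.1) ask whether hydroxychloroquine prevents disease, and Holm does not change the chance of showing this for at least one dose. The plan does not say that both doses are expected to work. Its 310 anticipated events happen to equal 1165 × (0.10 + 0.10 + 0.0662) = 310.1, with one dose inactive and no loss; both doses active would give 1165 × (0.10 + 2 × 0.0662) = 271. The plan does not state that derivation, but if one dose is inactive Holm adds nothing for the effective one.

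The change is not entirely free. Passing alpha on requires a second boundary set. After an efficacy halt and open-label conversion there may be no blinded placebo follow-up in which to use it. The single-look figures for both doses therefore do not describe a trial that halts at the first crossing. In that case Holm still helps, but from a much lower base.

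A reader might infer from 10.4 that a pooled test is planned, or that analysis is by treatment received. The documents do not support either. Section 10.2 names the two comparisons and 10.4 says intention-to-treat, so the wording of 10.4 is a gap in clarity.

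**Conclusion.** The point holds as a cheap improvement. Holm keeps strong familywise control at two-sided 0.05 and never rejects less than the fixed split. If both doses have a hazard ratio of 0.65, it adds about 5 points per dose, and about 9 to 11 points for showing both doses at a single final look. The sizes rest on a 10% placebo risk, 1:1:1 allocation, a shared placebo group and a normal approximation, with loss varied from none to the full stated rates.

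Three stronger readings should be resisted. The fixed split does not inflate error. The 5 points are not unconditional: an effective dose gains essentially nothing beside a null one. And Holm does not cure the shortfall in 10.2: with the stated losses and both doses effective, power per dose rises from 71–73% only to about 76–78%, still below the stated 80%.

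**What to change.** In 10.4, name two intention-to-treat log-rank comparisons by randomised arm: once weekly against placebo and twice weekly against placebo. Test them by Holm at overall two-sided 0.05, with the smaller p-value against 0.025 and, if that is significant, the other against 0.05. Describe groups by assignment, not receipt. Label any pooled-active comparison as supportive.

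In 10.3, say that the 0.025 spending function applies to each comparison separately. Add a second set of boundaries for 0.05, used for the remaining comparison once the other null has been rejected.

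Reconcile this with 5.3.5 and the open-label conversion in 10.3. State that, after such a halt, the remaining comparison uses only the blinded data accrued up to that point.

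The cost is SAP wording, one boundary table and that reconciling sentence. No extra participants or data are needed. The starting power in 10.2 needs its own correction.
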